6.3. Treatment Assignment

All enrolled subjects will be randomized initially to Cohorts 1, 2, 3 and 4 such that upon reaching 12 subjects total for all 4 cohorts, each cohort will contain 3 subjects. The experience of these 12 subjects has guided the further conduct of the study. Adverse events, safety labs and the rate of infusion reactions in individual cohorts will dictate the continuance of a specific cohort. After the completion of at least one treatment cycle the subject experience will be evaluated before enrollment is opened to all cohorts. The future enrollment will be randomized between all open cohorts.

At this time Cohorts 1-10 are closed to enrollment. Randomization into the remaining open cohorts will continue until the cohorts are closed due to enrollment reaching 6-20 subjects per cohort or due to the stopping rules for individual cohorts. Cohorts that have closed due to enrollment levels may be re-opened to increase the enrollment to the maximum total number of subjects permitted.

6.3.1. Stopping Rules in an Individual Subject or in a Cohort

For this clinical trial a treatment period is defined as period of time from the beginning of dosing of the first study drug on a given dosing day (ie, Either saline placebo or SEL-110 during Part A of the study and SEL-037 during Part B of the study) to the beginning of the next scheduled dose of study drug, and has a typical duration of 28 days.

For Part C (Cohorts 13, 15, and 17), a treatment period is defined as the period of time from the beginning of dosing of SEL-212 to the beginning of the next scheduled dose of study drug.

Individual

For subjects in Cohorts 1 and 2, any subject who has a weekly serum uric acid value ≥ 6 mg/dl or $>50\%$ of their baseline (where baseline value refers to the pre-dose serum uric acid level from visit 4, Day 0, treatment period 1) at Day 21 of their current treatment cycle will not be eligible for the next dosing of SEL-037. The subject will be followed for 30 days post the last dose of study drug at which time they will have an End of Study assessment and their participation in the study will be terminated.

In Cohorts 3-8, 10-13, 15, and 17 only subjects whose ambient blood samples indicate a serum uric acid (sUA) value less than or equal to 1.0 mg/dL at any of the Day 21 visits will be eligible for the next dosing of SEL-212 (or SEL-037). All other subjects will be followed for 30 ± 2 days post the last dose of study drug at which time all of the End of Study assessments will be completed and their participation in the study will be terminated.

Cohort

If 5 subjects in any of Cohorts 1-5 or 7, or if 10 subjects in any of Cohorts 6, 8, 10, 11, or 12 have met the requirements for individual stopping of their participation in the trial as described above or have been stopped based on Section 6.4 then that cohort will no longer have any additional subjects enrolled in it. Those subjects who have been enrolled will continue until they fulfill the requirements

Study: SEL-212/201 Version: 7.1	Effective Date March 19, 2018
------------------------------------	----------------------------------

for individual stopping or complete the clinical trial treatment periods. If they continue to meet the requirements for continued participation they may continue in Part B of the study.

In Part C, if 10 subjects in either of Cohorts 13, 15, or 17 have met the requirements for individual stopping of their participation in the trial as described above or have been stopped based on Section 6.4 then the cohort will no longer have any additional subjects enrolled in it. Those subjects who have been enrolled will continue until they fulfill the requirements for individual stopping or complete the clinical trial treatment periods. If they continue to meet the requirements for continued participation they may continue in the clinical trial.

The medical monitor, Investigator, IRB, or regulatory agency may also stop additional dosing or dose escalation based on any condition that warrants termination such as the discovery of an unexpected, serious or unacceptable risk to subjects or an unacceptable incidence of an expected event (e.g., unacceptable incidence or severity of infusion reactions) which suggests additional dosing is not warranted.

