- Frequency summary of subjects for ADA positive and negative results on day 21 as well as titer groups stratified by stopping rule from the protocol - subjects who had serum uric acid (sUA) value less than or equal to 1.0 mg/dL at any of the Day 21 visits and were eligible for the next dosing of SEL-212 (or SEL-037) vs subjects who had > 1mg/dL sUA at this time point. The results for the treatment periods will be time-matched between immunogenicity testing and sUA concentration measurement. The data will be presented by cohort and overall.
- Additionally model for the evaluation of the dose effect of SEL-110 and SEL-037 on PD results described in the section 9.6 of the SAP may be repeated with additional covariate for immunogenicity (cumulative positive, negative, positive low, high and moderate titer) to evaluate if immunogenicity had an additive or individual effect on the sUA as compared to the dose effect.

Following plots will be presented for immunogenicity and PK parameters:

Box and whiskers plot for comparison of CL values for SEL-037 (pegsiticase), C_{\max} , T_{\max} , AUC_{0-last} , and AUC_{0-inf} derived using both PK concentrations and uricase activity between subjects with cumulative positive and negative immunogenicity results for each antigen separately (PEG, uricase or pegsiticase) by Cohort with varying doses of SEL-110 and overall. The additional plots will be created for the Part C.

Following plots will be presented for immunogenicity and PD parameters:

Box and whiskers plot for comparison of C_{\min} , CFB_{\min} , $AUE_{CFBlast}$ and $TA_AUE_{CFBlast}$, $\%CFB_{\min}$, $AUE_{\%CFBlast}$ and $TA_AUE_{\%CFBlast}$ values for uric acid between subjects with cumulative positive and negative immunogenicity results for each antigen separately (PEG, uricase or pegsiticase) by cohort and overall.

Statistical Analysis Plan

10.5. ASSESSMENT OF THE EFFECTS OF IMMUNOGENICITY OF PHARMACOKINETICS OF SEL-037(PEGSITICASE) AND ON PD PARAMETERS OF URIC ACID

The effect of possible antibody responses on PK parameters will be evaluated descriptively.

Immunogenicity results will be compared descriptively between treatments using frequency of each type of ADA as main parameter as well as the time of onset of immunogenicity.

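### SAP 10.4 stratifies its Day 21 antibody table by the protocol stopping rule but uses only the 1.0 mg/dL gate, which does not apply to Cohorts 1 and 2

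*Protocol*

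**What the plan says.** Protocol 6.3.1, repeated in the Synopsis, contains two individual stopping rules.

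- **Cohorts 1 and 2 (SEL-037 alone).** The rule opens "For subjects in Cohorts 1 and 2, any subject who has a weekly serum uric acid value ≥ 6 mg/dl" and adds an alternative limb at more than 50% of baseline, where "baseline value refers to the pre-dose serum uric acid level from visit 4, Day 0, treatment period 1". A subject who meets either limb "at Day 21 of their current treatment cycle will not be eligible for the next dosing of SEL-037".
- **All SEL-110-containing cohorts.** The rule opens "In Cohorts 3-8, 10-13, 15, and 17 only subjects whose ambient blood samples indicate a serum uric acid (sUA) value less than or equal"; the limit is 1.0 mg/dL at Day 21, and subjects within it may receive the next dose. Cohorts 1 and 2 are not on this list.

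SAP 10.4, third bullet in the list of immunogenicity tables, plans a frequency summary of Day 21 antibody status "as well as titer groups stratified by stopping rule from the protocol". One stratum is "subjects who had serum uric acid (sUA) value less than or equal to 1.0 mg/dL at any of the Day 21 visits" who "were eligible for the next dosing of SEL-212 (or SEL-037) vs subjects who had > 1mg/dL sUA at this time point"; the closing words of that quote are the other stratum. The bullet asks for the data by cohort and overall, and says that results will be time-matched by treatment period between antibody testing and uric acid measurement.

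SAP Sections 10 and 10.1 include Cohorts 1 and 2 in the immunogenicity analysis. Their stopping rule does not appear in the SAP text supplied, and SAP Section 13 declares no change from the protocol's planned analysis.

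**The concern.** The table claims to show antibody status against the protocol's own decision to continue or stop. In the SEL-110 cohorts the 1.0 mg/dL split is that decision. In Cohorts 1 and 2 it is not: a subject can exceed 1.0 mg/dL and still qualify for the next dose. One row label then means different things in different cohorts, and the overall summary mixes the two.

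Immunogenicity of SEL-037 with and without SEL-110 is a secondary objective, and Cohorts 1 and 2 are the only arms without SEL-110. This is also the one planned table that ties antibody status to eligibility for the next dose. With cohorts planned at 6 to 20 subjects, moving one or two people between strata would visibly change a cohort percentage.

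**Working it through.** No sample size or power figure is in dispute, so the check compares the two rules directly.

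**Inputs**
- Cohort 1-2 rule (Protocol 6.3.1): not eligible if Day 21 sUA ≥ 6 mg/dL or > 0.5 × baseline. I read both limbs as applying to the Day 21 value.
- SAP 10.4 split: sUA ≤ 1.0 v > 1.0 mg/dL.
- Baseline: the Period 1 Day 0 pre-dose value. The documents give only the entry requirement of at least 6 mg/dL at screening, so Day 0 baselines of 6 to 14 mg/dL are an assumed range.

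**Step 1. Discordant band.** A Cohort 1-2 subject is eligible under the protocol but in the SAP's upper stratum when sUA > 1.0, sUA < 6 and sUA ≤ 0.5 × baseline.

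| Assumed baseline (mg/dL) | 0.5 × baseline | Eligible for re-dosing but tabulated as > 1 mg/dL |
|---|---|---|
| 6 | 3.0 | > 1.0 to 3.0 |
| 8 | 4.0 | > 1.0 to 4.0 |
| 10 | 5.0 | > 1.0 to 5.0 |
| 12 | 6.0 | > 1.0 to < 6.0 (the 6 mg/dL limb binds) |
| 14 | 7.0 | > 1.0 to < 6.0 (the 6 mg/dL limb binds) |

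The band exists whenever 0.5 × baseline > 1.0, that is, for any baseline above 2.0 mg/dL.

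**Step 2. A single case.** Baseline 8, Day 21 sUA 3.0: 3.0/8 = 37.5% of baseline, and below 6. The protocol allows the next dose; the SAP puts the subject opposite the eligible stratum.

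**Step 3. Reverse error.** Being stopped under the Cohort 1-2 rule at sUA ≤ 1.0 would need 0.5 × baseline < 1.0, a baseline below 2.0. It does not arise in the assumed range, so misplacement goes one way.

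**Step 4. Effect on the antibody contrast.** Take 12 subjects, all counts assumed: 2 at or below 1.0 and ADA-negative, 3 in the band, 7 stopped and ADA-positive. ADA-positive fractions are:

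| Band subjects | SAP split: > 1.0 v ≤ 1.0 | Own-cohort rule: not eligible v eligible |
|---|---|---|
| All ADA-negative | 7/10 (70%) v 0/2 | 7/7 (100%) v 0/5 |
| All ADA-positive | 10/10 (100%) v 0/2 | 7/7 (100%) v 3/5 (60%) |

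In the first case the SAP split shows a weaker contrast than the protocol rule would (70 v 100 percentage points); in the second, a stronger one (100 v 40). The direction depends on the antibody status of the band subjects, which the documents do not give.

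**The case against.** The best defence is that the SAP names its second stratum by a uric acid value and does not call it stopped. A Cohort 1 subject at 3 mg/dL is correctly counted under that literal label, and a common cut-off keeps cohorts comparable. This stands in part: a common 1.0 mg/dL split is a legitimate display. What fails is calling it the protocol stopping rule and defining the other stratum by eligibility, because neither is true for Cohorts 1 and 2. It is also fair that a cohort-specific rule makes the overall row pool two definitions of failure; that follows from the protocol and can be footnoted.

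Three stronger readings are tempting and should not be drawn.

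- **The table understates the link between antibodies and loss of response.** That needs band subjects to be ADA-positive less often than stopped subjects. Protocol 4.3.2.1 reports that in the first SEL-037 study antibodies generally went with faster clearance and reduced activity at Day 14, so a partial rebound by Day 21 could itself be antibody-related. The bias could go either way.
- **The strata overlap, so a subject who passes in Period 1 and fails in Period 2 is counted in both.** The first stratum's wording invites this, but the time-matching sentence in the same bullet points to a per-period table, in which that subject counts once in each period. Only a wording tension remains.
- **At least 12 subjects are misplaced.** Two cohorts at the planned minimum of 6 make 12 subjects in total, but that is neither a count of those in the band nor a guaranteed enrolment, since a cohort may close under the stopping rules.

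Other outputs also limit the damage. SAP 10.4 summarises Day 21 uric acid by antibody status and titer group, and SAP 10.5 compares PD parameters by antibody status within cohort, without inference.

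**Conclusion.** The mismatch is real, and I found nothing in either document that cures it. As written, the Cohort 1 and 2 rows and the overall summary do not show status under the protocol stopping rule. That conclusion rests on the text alone; only the width of the band depends on assumed baselines.

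The consequence is small. It is confined to one descriptive table for a secondary objective and to re-dosed Cohort 1-2 subjects with Day 21 sUA above 1.0 mg/dL; those at or below 1.0 are placed correctly. The number affected and the direction of any distortion cannot be known from the documents. The primary safety analysis, the dosing decisions and the planned PD contrasts do not use this table. Nothing here bears on which clinical threshold is right.

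**What to change.** In the third bullet of SAP 10.4, define the strata for each treatment period as eligible v not eligible for the next dose under the individual rule that Protocol 6.3.1 sets for the subject's own cohort. Footnote the two rules under the overall summary.

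Alternatively, keep the common 1.0 mg/dL split, label it as an sUA threshold and not as the stopping rule, and leave Cohorts 1 and 2 out of any overall stopping-rule summary.

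In either case, replace the reference to any Day 21 visit with 'at the Day 21 visit of that treatment period', so that it agrees with the time-matching sentence already in the bullet.

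The cost is SAP wording and the matching table shell. Day 21 sUA, baseline sUA and dosing records are already collected, and no protocol change is needed.

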6. GENERAL ASPECTS FOR STATISTICAL ANALYSIS

6.1. GENERAL METHODS

SAS® version 9.3 will be used for all statistical analyses and tabulations.

In general, summaries will present data by treatment/cohort and assessment time where appropriate. Unless stated otherwise, descriptive summaries will include n, mean, standard deviation, median, minimum, and maximum for continuous variables, and n and percent for categorical variables. If there are multiple assessments collected on the same scheduled time within the windows, the average of these assessments will be used. For tabulated safety summaries, only the scheduled assessments will be included in the summary tables.

Data collected at unscheduled visits will be included in the data listings but will not be included in the analyses. The data for the EOS visit at day 140 will be separated from the Early Termination visit data and will be summarized for all the subjects within the defined population who reached this visit. An additional observational visit for subjects with <6 mg/dL uric acid concentration on day 140 (approx. 30 days after last dose) were scheduled at approx. 170 days from 1st dose. The data for the observational visit will be reported and summarized for all subjects participating in this visit. Data for Early Termination visits will be listed with actual day from dose included and will not be summarized. The last result for repeat test at screening visit will be considered as final and will be included in summaries. Previous results will be listed but not summarized.

Adverse events and medical history will be coded according to the most recent Medical Dictionary for Regulatory Activities (MedDRA) version. Prior and concomitant medications will be coded using the most recent WHO Drug Dictionary version.

Derivation of PK parameters will be performed using Phoenix WinNonLin 6.4 or higher on a Windows 7 platform or higher.

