9.4. DATA SUMMARIZATION

PD parameters and serum concentration data will be summarized by Treatment period and Cohort using the following descriptive statistics:

PD Summary Statistics:

Variable	Summarized with:
Serum concentration at each nominal time point	n, number and % BLQ, arithmetic mean, SD, CV%, minimum, median and maximum
CFB _{min} , %CFB _{min} , AUE _{CFBlast} , AUE _{%CFBlast} and TA_AUE _{CFBlast} , TA_AUE _{%CFBlast}	n, arithmetic mean, SD, CV%, minimum, median, maximum, geometric mean and geometric CV%
T _{onset} , T _{resolve} , T _{duration} , and T _{min} (actual time)	n, minimum, Q1, median, Q3 and maximum

Mean concentrations will not be presented if 50% or more of the available observations relative to total number of subjects within the treatment at any time point are missing. BLQ values for uric acid concentration will be summarized as 0 (zero) for all time points.

Samples taken outside the allowed time windows may be excluded from summarization. This will be determined prior to database lock.

The following conventions will be used for the presentation of the descriptive statistics of PD parameters and serum concentrations for uric acid:

Statistical Analysis Plan

PD Reporting Precision:

Statistics	Degree of Precision
Minimum, Maximum	3 significant digits or as needed based on actual measured values (for example PD concentrations)
Mean (arithmetic and geometric), Median	4 significant digits or as needed based on actual measured values (for example PD concentrations)
Standard deviation	5 significant digits or as needed based on actual measured values (for example PD concentrations)
CV, Geometric CV	1 decimal point or as needed based on actual measured values (for example PD concentrations)

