Mean time response profiles for uric acid concentration raw values and %CFB at each time point for each Treatment period and cohort plotted against time for each Cohort separately with curves for all Treatment periods overlaid on one plot. BLQ values for uric acid concentration will be assigned 0 values for linear scales and 1/10 of LLOQ values for all time points for the graphic representation on log-linear scales only. Actual measured concentrations will be presented on both linear and log-linear scales while %CFB profiles will be presented on linear scale only.

Box plots for each derived PD parameter based on actual measurements and %CFB: CFB_{min}, AUE_{CFBlast}, TA_AUE_{CFBlast} will also be plotted by treatment.

Individual profiles for uric acid concentration absolute values and %CFB will be plotted for each Treatment period and cohort on a separate plot.

9.7. ASSESSMENT OF THE EFFECTS OF SEL-110 (RAPAMYCIN) AND SEL-037 (PEGSITICASE) ON PD PARAMETERS OF URIC ACID

Assessments done outside the assessment windows may be excluded from summarization. This will be determined prior to database lock.

The key PD parameters based on measured values and %CFB %CFB_{min}, AUE_{%CFBlast}, and TA_AUE_{%CFBlast} as well as uric acid concentration and %CFB on day 21 of each treatment period will be analyzed using linear mixed model for the response to SEL-110 dose levels co-administered with either 0.2 or 0.4 mg/kg of SEL-037 (the dose level of SEL-110 for Cohorts 1 and 2 will be assigned as 0). Additionally contribution of SEL-110 to the PD effect of SEL-037 will be tested to compare the following (test - reference). For PD

Statistical Analysis Plan

parameters based on actual measured values baseline concentration of uric acid will be incorporated in the model as covariate.

For Parts A and B following contrasts will be tested:

Cohort 3 Part A vs Cohort 1 Part A
Cohort 5 Part A vs Cohort 1 Part A
Cohort 7 Part A vs Cohort 1 Part A
Cohort 4 Part A vs Cohort 2 Part A
Cohort 6 Part A vs Cohort 2 Part A
Cohort 8 Part A vs Cohort 2 Part A
Cohort 10 Part A vs Cohort 2 Part A
Cohort 12 Part A vs Cohort 2 Part A
Cohort 1 Part A vs Cohort 2 Part A
Cohort 3 Part A vs Part B
Cohort 5 Part A vs Part B
Cohort 7 Part A vs Part B
Cohort 4 Part A vs Part B
Cohort 6 Part A vs Part B
Cohort 8 Part A vs Part B
Cohort 10 Part A vs Part B
Cohort 12 Part A vs Part B

For Part C (cohorts 13, 15, 17) additional contrasts will be:

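### Cohorts 1-2 are re-dosed under a looser Day 21 uric acid limit than the SEL-212 cohorts, so Period 2-3 summaries and the visit 22 share compare differently selected survivors

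*Protocol*

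**What the plan says.** Protocol 6.3.1 has two individual continuation rules. In the SEL-212 cohorts, "only subjects whose ambient blood samples indicate a serum uric acid (sUA) value less than or equal to 1.0 mg/dL" at Day 21 receive the next dose. The other rule begins "For subjects in Cohorts 1 and 2, any subject who has a weekly serum uric acid value ≥ 6 mg/dl", and its second limb stops anyone above 50% of the Period 1 pre-dose value. Stopped subjects have a final assessment about 30 days after their last dose and leave.

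The SAP then does the following:
- **6.1:** "Data for Early Termination visits will be listed with actual day from dose included and will not be summarized".
- **9.3.1:** missing PD values are taken as uninformative and are not imputed.
- **9.4:** "PD parameters and serum concentration data will be summarized by Treatment period and Cohort". The one guard is "Mean concentrations will not be presented if 50% or more of the available observations relative to total number of subjects within the treatment" are missing at a time point.
- **9.6:** a table gives the share below 6 mg/dL at visit 22. A second table uses a subset whose criteria do not mention sUA stops.
- **9.7:** "uric acid concentration and %CFB on day 21 of each treatment period will be analyzed using linear mixed model". Cohorts 3, 5 and 7 are contrasted with Cohort 1, and Cohorts 4, 6, 8, 10 and 12 with Cohort 2, all at Part A level. A geometric mean ratio outside 80-125% is read as a SEL-110 effect.
- **10.4:** an antibody table is "stratified by stopping rule from the protocol - subjects who had serum uric acid (sUA) value less than or equal to 1.0 mg/dL", by cohort and overall. The Cohort 1-2 rule is not given.
- **15.2.5.2:** unless otherwise noted, percentages use subjects with an observation.

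**The concern.** Cohorts 1-2 are the only arms that never receive SEL-110. They are the reference for its contribution to the PD effect, which belongs to a secondary objective. After the first Day 21 check, a subject at 2 mg/dL, or up to the personal limit, stays in Cohorts 1-2 but leaves a SEL-212 cohort. If response is correlated within subject, SEL-212 survivors look better later even when SEL-110 does nothing. The difference then mixes the drug effect with who was allowed to stay. In the SAP 10.4 table, such a Cohort 1-2 subject falls in the stratum above 1.0 mg/dL although re-dosed.

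**Working it through.** The plan gives no figure on this point, so there is nothing to reproduce. Steps 1, 2 and 6 are arithmetic or logic. The sizes in steps 3 and 4 rest on assumed inputs.

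**1. The two limits.** Inputs: Protocol 6.3.1 and the screening criterion of sUA ≥6 mg/dL (7.1). The Cohort 1-2 limit is the smaller of just under 6 and 0.5 × baseline: 3.0 at baseline 6, 4.0 at 8, 5.0 at 10, just under 6 at 12 or more. The SEL-212 limit is 1.0. The ratio is 3 to nearly 6. The rule is read per period, the natural reading.

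**2. Where selection enters.** Period 1 Day 21 follows no check, Period 2 follows one and Period 3 two. Visit 22 is the Period 4 dosing visit (Protocol Table 4), so it follows three.

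**3. Null simulations.** The drug effect is the same in both arms; only the limit differs. Baseline is normal(8.5, 1.3), at least 6, in both models.
- *Model A:* correlated Day 21 values; 55-80% at ≤1.0 mg/dL in Period 1 and 5-20% between the limits; 60,000 per arm.
- *Model B:* exponential time to loss of response (mean 30, 60 or 120 days), then return to baseline over a median 14, 28 or 56 days; 400,000 per arm.

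| SEL-212 vs Cohorts 1-2 | A, correlation 0.3-0.8, no drift | B, nine scenarios |
|---|---|---|
| Period 2 mean sUA, mg/dL | 0.01-0.51 lower | 0.35-1.46 lower |
| Period 3 mean sUA, mg/dL | 0.07-0.50 lower | 0.35-2.13 lower |
| Visit 22 <6, observed subjects | 95-100% vs 94-97% (1-4 points higher) | 97.6-100% vs 89.0-99.4% (0.6-8.6 higher) |
| Visit 22 <6, all dosed | 23-68% vs 28-80% (4-32 lower) | 8.0-55.6% vs 8.9-68.1% (0.9-16.2 lower) |

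At correlation 0, model A shows no Period 2 gap. In the middle case of B (60 and 28 days), Period 1 means are 1.18 in both arms and Period 2 means are 2.07 vs 3.06.

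The denominator sets the direction at visit 22. In A with correlation 0.6, 60% at ≤1.0 and 20% between the limits, 38% of SEL-212 and 63% of Cohort 1-2 subjects pass three checks; 38% and 61% of all dosed are below 6 at visit 22. Over observed subjects that is 38/38 = 100% vs 61/63 = 97%. Over all dosed it is 38% vs 61%.

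**4. Part A contrast.** Random-subject model on log Day 21 sUA; the true ratio is 1.00. Drift in A is 0.3 latent SD per period. B used 4,000 per arm with baseline as covariate; ratio = exp(log difference), for example exp(-0.507) = 0.60.

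| Fixed effects | A, no drift | A, upward drift | A, downward drift | B |
|---|---|---|---|---|
| Treatment | 1.00-1.03 | 0.89-0.98 | 1.03-1.15 | 0.60-0.92 |
| + period | not given | 1.00-1.03 | 1.02-1.07 | 0.83-1.00 |
| + treatment-by-period, at Period 1 | not run | not run | not run | 0.96-1.07 |

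A period main effect is nearly enough in A but not in B.

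**5. The 50% rule.** With 10 dosed, a mean is shown only if at least 6 remain. The binomial chance of that is 0.6, 17, 38, 63 or 85% when the true share continuing is 20, 40, 50, 60 or 70%. The rule covers mean concentrations, not medians, PD parameters or visit 22 counts.

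**6. A common definition.** A value ≤1.0 mg/dL satisfies both rules unless baseline is below 2. So success defined as ≤1.0 at all three Day 21 visits and below 6 at visit 22, over all dosed, can be observed alike in every cohort. Three examples from A give 29/29, 38/38 and 56/56%. Restricting all cohorts to records whose earlier Day 21 values were ≤1.0 brings the Period 2-3 gaps in A within 0.05 mg/dL of zero.

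**The case against.** A reader might infer that the SAP omits a period term. The documents do not support that. The model statement is labelled example code and also leaves out the baseline covariate that the text of SAP 9.7 requires. The Part C contrasts are by period, so the treatment factor may carry period. The fair criticism is that Part A coding is unclear, although Part A-level contrasts with a random subject term point to pooling.

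A reader might also infer that the visit 22 denominator is undefined. SAP 15.2.5.2 has a default, subjects with an observation, alongside a general caution about choosing denominators. Simply switching to all dosed subjects would reverse the lean, and in most scenarios enlarge it.

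The reference means may seldom appear. Protocol 4.3.2.1 reports that in 22 subjects on SEL-037 alone the effect lasted to Day 7 in all but one and to Day 30 in one; Day 21 is not reported. If 20-40% of Cohort 1-2 subjects continued, the 50% rule would usually suppress their Period 2 mean. That stands, but the other outputs would remain, on few subjects.

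Finally, safety is the primary objective, no PD comparison is powered, and the period and visit 22 tables are descriptive. Period 1, Cohort 1 vs 2, and the Part C contrasts with Cohort 11 each share one rule or precede it. All of that stands and limits the stakes. It does not make the later-period comparisons like for like.

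**Conclusion.** The concern holds for Period 2-3 sUA summaries and the visit 22 share when set against Cohorts 1-2. Under the default denominator the SEL-212 visit 22 share is near 100% by selection and leans towards SEL-212; over all dosed subjects it leans the other way. The Part A contrasts may shift if periods are pooled, by an amount and, under some drift assumptions, a sign that the documents do not settle.

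The size is not established. It needs some subjects between the two limits and within-subject correlation or progressive loss, and the documents quantify neither. Models A and B agree on direction for the summaries and visit 22 but differ on magnitude.

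It would be too strong to infer that an apparent SEL-110 effect is an artefact, or that false positives follow. In model A with 10 dosed per cohort and no drift, the Period 2 difference has an SD of 0.6-1.5 mg/dL and rejects in 3-5% of runs. Estimates shift; the test does not reject too often.

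**What to change.** 1. **SAP 9.7:** fit Day 21 sUA of Periods 1-3 jointly, keeping all observed Day 21 values, with period and treatment-by-period terms. Report the Period 1 contrast as the comparison with Cohorts 1-2 that is free of the stopping rule. Do not rely on a period main effect alone.
2. **SAP 9.6:** keep the existing table below 6 mg/dL and state its denominator. Add a supplementary share over all dosed subjects, with success in every cohort defined as in step 6 of the working, and use it for comparison with Cohorts 1-2.
3. **SAP 9.4:** label Period 2-3 comparisons with Cohorts 1-2 as conditional on retention under different rules. Add a sensitivity version that keeps a later-period record only if all that subject's earlier Day 21 values were ≤1.0 mg/dL.
4. **SAP 10.4:** footnote that Cohorts 1-2 were re-dosed under the other rule.

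Stopping rules and safety data are unchanged. The cost is two model terms, one record flag (SAP 10.4 already needs the 1.0 mg/dL split), one table and some labels. The Period 1 contrast speaks only to the first dose. The sensitivity version has fewer Cohort 1-2 records and still compares selected subjects if SEL-110 works. The supplementary share is stricter than the 6 mg/dL target and should be read only as a like-for-like comparison.
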